8.2 Endpoints

8.2.1 Primary Endpoints

The primary endpoint of the study will be the proportion of patients with recovery in their MS related disability measured at 8 weeks through the Functional Systems Scores of the EDSS (Visual, Brainstem, Pyramidal, Cerebellar, Sensory, Bowel/Bladder and Ambulation score). The subgroup of 40 patients without relapse will not be evaluated for the primary endpoint.

8.2.2 Secondary Endpoints

The secondary endpoints of the study will be:

- Proportion of patients with recovery in their MS related disability measured at 12 and 24 weeks through the FSS of the EDSS (Visual, Brainstem, Pyramidal, Cerebellar, Sensory, Bowel/Bladder and Ambulation score);
- MS-related disability and cognitive impairment measured through the 25-FWT, the 9HPT, the Symbol Digit Modalities Test and the Low Contrast Letter visual Acuity Test (Polman and Rudick, 2010; Drake et al, 2010) during a clinical relapse at 8, 12 and 24 weeks;
- Fatigue, measured through the MFIS (Fisk et al, 1994) and the Fatigue Severity Scale (Krupp et al, 1989), at baseline during a clinical relapse and 8, 12 and 24 weeks after the onset of the relapse;
- LTP through TMS at baseline and 8, 12 and 24 weeks after the beginning of treatment, in patients without relapse;
- Immune-metabolic response of the lymphocytes in treated patients *in vitro* (glycolysis, mitochondrial respiration, fatty acids oxidation and circulating adipocytokines).

8.2.3 Other Endpoints

The following safety parameters will be evaluated:

- Incidence, severity, and relationship to treatment of treatment-emergent adverse events (TEAEs);
- Incidence, severity, and relationship to treatment of SAEs;
- Clinically significant changes in routine haematology, chemistry and urinalysis laboratory tests;

C
C
I

8.3 Analysis Sets

Intention-to-treat (Full Analysis Set)

The intention-to-treat (ITT) population will include all patients enrolled into the study and assigned to the randomised treatment.

Per-protocol

The per-protocol (PP) population will include all patients who have been treated according to protocol and fulfil the following criteria:

- Compliance with all entry criteria;
- Absence of major protocol violations;
- Adequate compliance with study medication.

Safety

The safety population will include all patients who have received at least one dose of planned study treatment.

The number and percentage of the patients included in the analysis populations will be reported in a table showing the reason of exclusion for all patients enrolled into study.

The efficacy analysis will be performed in the ITT population. In order to assess the robustness of the results, the analysis of the primary endpoint will be repeated in the PP population.

The safety analysis will be performed in the safety population.

8.4 Description of Statistical Analyses

8.4.1 General Considerations

Methods described here represent the outline of the intended methods.

A Statistical Analysis Plan (SAP) will be produced before the database lock and will contain full details of all planned summaries, listings and analyses.

All summaries and listings will be performed using Statistical Analysis Software (SAS) System software (version 9.2 or later). Unless otherwise specified, all statistical hypotheses will be tested at the 5% significance level ($\alpha = 0.05$) against two-sided alternatives, and corresponding 95% confidence intervals (CI) will be reported as appropriate.

For endpoints measured over time, descriptive statistics (for continuous variables) or frequency count (for categorical data) will be summarized by each time point.

Demographic and clinical characteristics at baseline will be summarized as frequency distributions (for categorical variables) and descriptive statistics of mean, standard deviation, median, minimum and maximum (for continuous variables).

All collected variables will be tested for normality and homogeneity of variance by using Kolmogorov Smirnov and Levene tests.

8.4.2 Analysis of Primary Endpoint

The comparison between the proportions of recoveries at 8 weeks in patients treated with D-aspartate and patients treated with placebo will be based on descriptive statistics (difference, relative risk and/or odds ratio) and on the chi-square test.

A set of exploratory analyses is planned. First, a multiple logistic regression model will be fitted to the data with recovery at 8 weeks as the dependent variable and age, sex, current DMT use, disease course, severity of relapse, and random assignment as covariates, to adjust for imbalances between the treatment groups.

Second, the time to recovery will be computed for each patient and included as the dependent variable in a multivariate Cox model, with all the above mentioned variables as covariates. Patients not recovered will be censored at last observation.

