5.1 Overall Study Design and Plan

This Phase II study will be a prospective, parallel group, double blind, balanced randomised block, placebo-controlled study. The study is expected to start on December 2017 (first patient in) and to end on December 2020 (Clinical Study Report).

The study will be conducted according to the plan presented in Figure 1.

Figure 1. Study plan

Note: the first randomisation (from a specific randomisation list) will involve 10 sites, which will not be involved neither in the immunological analyses nor in TMS; the second randomisation (from a specific randomisation list) will involve only the sites of Rome, Naples and Pozzilli (Isernia), which will collect the blood samples for the immunology analyses, and the third randomisation (from a specific randomisation list) will involve site of Pozzilli for patients without relapse, which will perform the TMS.

The study will be carried out in approximately 18 investigational sites in Italy.

Patients will be recruited from the following 3 MS centres of the 5 Steering Committee members reported in Section 2: PPD

and from other approximately 16 qualified MS centres that will participate to the study.

A number of 120 MS patients presenting with a relapse or not will be randomised to receive either D-asp 2660mg once daily or placebo as add-on to conventional therapies (IFN beta-1a 44mcg TIW for patients without relapse and IFN beta-1a 44mcg TIW plus methylprednisolone i.v. for patients with relapse, for 5 consecutive days at 1000mg once daily).

The TMS will be performed only in the scheduled 40 patients without relapse enrolled in the MS centre of the PI

Immune-phenotype and immune-metabolic response of lymphocytes will be evaluated in 80 patients, which will include 40 patients with relapse enrolled in the sites of Rome, Naples and Pozzilli, and 40 patients without relapse enrolled in the site of Pozzilli. This distribution will allow to measure immunological parameters in a balanced way among patients with D-asp and placebo. Patients that will perform immunological parameters will be randomised separately from those recruited in the other centres (which will enrol only patients with relapse that will be randomised to receive D-asp/placebo and will not perform immunological assessments).

Determinations of immunological parameters will be performed in the laboratory IEOS-CNR in Naples on fresh blood.

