D-asp at the dose of 2660mg or placebo will be administered once a day for 24 weeks in the form of identical oral solution preparations. The IP (D-asp or placebo) should be administered preferably after the meal.

The content of a sachet should be cleared out in an empty glass. Then approximately 100 ml of still water should be added and the product should be mixed until the effervescence is ended. The product should be administered immediately after the preparation.

Placebo will be undistinguishable from D-asp in terms of packaging, size, colour, weight, appearance, taste and mode of administration.

6.3

Assignment to Treatment Groups

Patients presenting with a relapse and meeting the eligibility criteria during a screening period of 3-5 days will be randomised in a 1:1 ratio via e-CRF to:

- D-asp,
- Placebo.

It is planned to randomise 80 patients with relapse. Randomisation will be stratified according to age (<30 years vs. \geq 30 years) and site location (Rome+Naples+Pozzilli vs. the other sites).

Patients without a relapse will be recruited only at the Pozzilli site and will be randomised in a 1:1 ratio via e-CRF to:

- D-asp,
- Placebo.

It is planned to randomise 40 patients without a relapse. Randomisation will be stratified according to age (<30 years vs. \geq 30 years)

The randomisation list will be in a balanced block design and will be centralized. In each site, eligible patients will be sequentially assigned to the next study number as they present themselves for the study, starting from the lowest number provided for each centre. If a patient discontinues from the study, the patient number will not be reused, and the patient will not be allowed to re-enter the study.

It will be the responsibility of the Investigator (or designee) to explain, and make sure patients fully understand any appropriate treatment related information.

6.4

Non-investigational Medicinal Products to be Used

Treatment with the IP (D-asp 2660mg once daily or placebo) will be administered as add-on to conventional therapies (IFN beta-1a 44mcg TIW for patients without relapse and IFN beta-1a 44mcg TIW plus methylprednisolone i.v. for patients with relapse, for 5 consecutive days at 1000mg once daily).

The prescription of IFN beta-1a in the individual patients will be totally independent from his/her inclusion in the study.

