8.1 Sample Size

The primary study endpoint in the part of the study focused on relapsed patients is defined as the proportion of patients who, following a disease relapse associated with a worsening in their MS-related disability, return to baseline status within 8 weeks. Disability will be assessed through the Functional Systems Scores of the EDSS (Visual, Brainstem, Pyramidal, Cerebellar, Sensory, Bowel/Bladder and Ambulation score).

Available data from observational studies (Hirst et al, 2012) indicate that approximately 50% of the patients return to baseline EDSS within 2 months with standard treatments. Based on the fact that usually, in clinical studies where a rigid intention-to-treat (ITT) approach is used, a lower rate of responses/recoveries is observed as compared to observational studies, the expected rate of recovery at 2 months in the control group is set at 40%. With 40 patients per arm the study will be able to detect with 80% power, at the 0.05 alpha level (1-sided), an increase in the proportion of recovery at 2-months from 40% to 70%. The 1-sided significance level is justified by the exploratory nature of this study, aimed at generating study hypotheses to be tested in subsequent studies.

A total of 120 patients will be randomised to include the 40 RR-MS patients without relapses. This subgroup of patients without relapse has been included to assess whether D-Aspartate enhances LTP induction, by means of TMS

Refer to Section 6.3 for procedures of randomisation.

Eligible patients at the end of the screening period will be randomised in a 1:1 ratio to D-asp or placebo. Randomisation will be stratified according to age (<30 years vs. \geq 30 years) and site location (Rome+Naples+ Pozzilli vs. the other sites).

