8.4.3 Analysis of Secondary Endpoints

The comparison between the proportions of recoveries at 12 and 24 weeks in patients treated with D-aspartate and patients treated with placebo will be analysed as the main analysis of the primary endpoint.

To evaluate for differences after treatment, between groups in other secondary endpoints, repeated measures analysis of variance (ANOVA) will be used in case of parametric continuous variables, and Mann-Whitney and Kruskal Wallis tests will be used in case of non-parametric continuous variables. For repeated measures, ANOVA sphericity will be tested by using Mauchly's test and results corrected in case of need, by using Greenhouse-Geisser method. Significance level will be set at $p<0.05$.

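### The primary chi-square, reused at Weeks 12 and 24, ignores the age and site strata used in randomisation: valid, but conservative and less efficient if those strata predict recovery

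*Combined protocol and SAP*

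**What the plan says.** Section 6.3 randomises the 80 relapse patients 1:1, stratified by age (<30 vs >=30 years) "and site location (Rome+Naples+Pozzilli vs. the other sites"). It adds: "The randomisation list will be in a balanced block design and will be centralized". Section 8.1 repeats both factors, again naming "site location (Rome+Naples+ Pozzilli vs. the other sites"). Section 5.1 shows that the two site groups use different lists: the first list serves sites outside the immunology work, and "the second randomisation (from a specific randomisation list) will involve only the sites of Rome, Naples and Pozzilli (Isernia"). The third list is for patients without relapse, who do not enter the primary endpoint.

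For the analysis, Section 8.4.2 says the Week 8 comparison of recovery "will be based on descriptive statistics (difference, relative risk and/or odds ratio) and on the chi-square test". The Synopsis says the same. Under Section 8.4.3, recovery at Weeks 12 and 24 "will be analysed as the main analysis of the primary endpoint".

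The adjusted logistic and Cox models in 8.4.2 are labelled exploratory. They list age, but not site group. Section 8.4.1 defers full detail to a later SAP, and nothing tells that SAP to stratify.

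Section 8.4.2 gives no sidedness. Section 8.1 sizes the study "at the 0.05 alpha level (1-sided), an increase in the proportion of recovery at 2-months from 40% to 70" per cent. Section 8.4.1 tests by default "against two-sided alternatives, and corresponding 95% confidence intervals (CI) will be reported as appropriate".

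**The concern.** Randomising within strata balances the arms on those factors, so between-stratum differences in recovery no longer add to the variance of the treatment difference. A pooled chi-square still counts that variation as noise. If age or site group predicts recovery, the standard error is too large, the test rejects less often than its nominal 5% under the null, and the unstratified interval is less efficient than a stratified one. At stake is some precision in an 80-patient comparison made at three time points. Both factors are already known for every randomised relapse patient.

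**Working it through.** **Inputs from the protocol.** 40 relapse patients per arm, recovery 40% vs 70%, alpha 0.05 one-sided, 80% power (8.1); two strata factors with two levels each, so four strata (6.3, 8.1); 40 relapse patients planned at Rome, Naples and Pozzilli (5.1), hence 40 elsewhere.

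**The plan's own figure.** Without continuity correction, n = [1.645·√(2·0.55·0.45) + 0.842·√(0.24+0.21)]² / 0.30² = 32.9, so 33 per arm. With the correction, n = (32.9/4)·[1 + √(1 + 4/(32.9·0.30))]² = 39.3, so 40 per arm. The stated 40 is reproduced. At 40 per arm the uncorrected chi-square has exact power of 85.7% one-sided and 79.6% two-sided.

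**Why the pooled test is conservative.** Under the null with 1:1 balance in each stratum, the difference has variance (2/40)·Σw·p(1−p) over strata. The chi-square uses (2/40)·p̄(1−p̄), with p̄(1−p̄) = 0.24 at p̄ = 0.40. For two equal site groups:
- 50% vs 30%: (0.25+0.21)/2 = 0.23; ratio 0.23/0.24 = 0.958; effective critical value 1.645/√0.958 = 1.680; one-sided rejection about 4.6%.
- 60% vs 20%: (0.24+0.16)/2 = 0.20; ratio 0.833; effective critical value 1.802; rejection about 3.6%.

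**Why the interval narrows.** The unstratified 95% width at 40% vs 70% is 2·1.96·√(0.45/40) = 41.6 points. At 60% vs 20% with a common odds ratio of 4.50, the D-asp rates are 87.1% and 52.9% (mean 70%). Their mean within-stratum variance is (0.871·0.129 + 0.529·0.471)/2 = 0.1808, so the stratified width is 2·1.96·√((0.20+0.1808)/40) = 38.2 points.

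**Simulation.** The protocol gives no stratum recovery rates, age split or block size, so these are assumptions. There were 400,000 trials per scenario and layout, with the control average held at 40%, the D-asp average at 70% and a common odds ratio. Strata in order are Rome/Naples/Pozzilli <30 and >=30, then other sites <30 and >=30. The layouts were 20/20/20/20 and 10/30/10/30 with exact balance, and three with incomplete blocks: 11/29/9/31 (blocks of 4), 5/35/5/35 (blocks of 6) and 8/22/12/38 (blocks of 4). The uncorrected chi-square was compared with uncorrected CMH. Ranges are across layouts, in percentage points.

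| Control rates | Power change, one-sided | Power change, two-sided | Mean 95% CI width, unstratified vs Mantel-Haenszel |
|---|---|---|---|
| 40% throughout | 0 to +0.5 | −1.9 to +0.1 | 41.0 vs 41.0–41.1 |
| 45/35% by site | +0.2 to +0.7 | −1.6 to +0.1 | – |
| 50/30% by site | +0.8 to +1.2 | −0.6 to +0.3 | 41.0–41.1 vs 40.2–40.3 |
| 50/30% by age* | +0.6 to +1.0 | −1.7 to +0.2 | – |
| 60/40/40/20% (both) | +1.8 to +2.0 | +0.2 to +0.9 | 41.1 vs 39.3–39.8 |
| 60/20% by site | +3.2 to +3.7 | +2.6 to +3.1 | 41.1 vs 37.7–38.2 |

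*Separate runs of 200,000 trials; the one-sided range covers four of the five layouts.

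- Null rejection over the site and both-factor scenarios: chi-square 3.3–5.4%, CMH 4.6–5.3%. At 60/20%: 3.3–3.6% vs 5.0–5.1%.
- Power at 60/20%: one-sided 87.4–87.7% vs 90.6–91.3%; two-sided 81.3–81.7% vs 83.9–84.6%.
- The two-sided losses arise only with incomplete blocks. With no stratum effect, about half the loss reflects the chi-square rejecting 5.3–5.4% under the null. At a matched 5.0% size the powers are 78.8% vs 78.1%, 77.9% and 78.5% in the three incomplete-block layouts, a loss of 0.3 to 0.9 points.
- 95% interval coverage: unstratified Wald 93.9–95.9%, Mantel-Haenszel with Sato variance 94.0–94.5%.

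**The case against.** The strongest reply is that nothing here is an error. The pooled chi-square is valid, and one-sided its power exceeds the planned 80% in every scenario. Section 8.1 calls the study exploratory. No part of the protocol says that site group predicts recovery; the split is explained by where immunology samples are taken. The larger gains need control recovery of 60% in one site group and 20% in the other. With a spread of 20 points or less on one factor, the one-sided gain is at most 1.2 points. If the two-sided default applies, CMH can lose power, even with 50/30% by age. The later SAP could also add stratification.

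Most of this stands, and it limits the point to efficiency. It does not remove it. Section 8.4.2 names the test, 8.4.3 copies it, and neither the exploratory models nor the deferral to a SAP supplies a stratified comparison.

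Three stronger readings are tempting and not supported:
- That ignoring the strata inflates false positives. Rejection falls as the strata become prognostic; the 5.3–5.4% seen two-sided with no stratum effect is small-sample discreteness.
- That the unstratified interval is wrongly wide. The protocol names no interval method. A Wald interval covers about 94–95% except at 60/20%, where it covers 95.7–95.9%, so it is inefficient, not invalid. Part of the narrowing at 60/20% replaces slight over-coverage with slight under-coverage.
- That current DMT use and disease course are constants that must be deleted from the exploratory models. Eligibility suggests little variation, but 8.4.2 does not define them, and they could mean treatment duration or relapse history.

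**Conclusion.** The point holds as one of efficiency and of keeping the test near its nominal level. The primary test and risk difference do not use the randomisation strata, and the Week 12 and 24 comparisons inherit this. The cost ranges from almost nothing, if age and site group do not predict recovery, to 3 to 4 points of one-sided power and up to 3.4 points of interval width at 60% vs 20%. The gain is about 2 points of one-sided power if both factors matter. These sizes depend on assumed stratum rates, stratum sizes and block lengths.

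A reader might infer that stratifying always helps, or that it rescues an underpowered test. Neither follows. One-sided, the chi-square is already above 80% in every scenario; two-sided, CMH can lose up to about 2 points when blocks are incomplete and the strata are absent to moderately prognostic. The change is worth making before database lock, together with a decision on sidedness, because its effect on power depends on that decision.

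**What to change.** Replace the test sentence in Section 8.4.2 with wording such as:

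> Recovery at Week 8 will be compared by a Cochran-Mantel-Haenszel test without continuity correction, stratified by age (<30 vs >=30 years) and site group (Rome+Naples+Pozzilli vs other sites) as randomised. The Mantel-Haenszel risk difference will be given with a confidence interval using the Sato variance. Any relative risk or odds ratio will be the Mantel-Haenszel estimate. The unstratified chi-square is a sensitivity analysis.

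In the same paragraph, state the sidedness once: one-sided 0.05 as in 8.1 with a 90% interval, or two-sided 0.05 as in 8.4.1 with a 95% interval. Section 8.4.3 then applies the method at Weeks 12 and 24 without further change. Align the Synopsis.

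The SAP should note that a stratum with only one arm or only one outcome adds nothing to the CMH statistic, so small strata need no pooling rule for the test.

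Add site group to the exploratory logistic and Cox models. Either define current DMT use and disease course or drop them; dropping is optional.

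The cost is wording in the protocol and SAP before database lock, with no extra patients, visits or data. The price to accept knowingly is the possible two-sided power loss of up to about 2 points.

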- A urine pregnancy test will be performed in female patients to exclude pre-existing pregnancy (is not required if the patient is postmenopausal or surgically sterilized or if a serum pregnancy test was already performed within 7 days before the Baseline visit);
- Administration of the EDSS;
- Administration of the 25-FWT, the 9HPT, the Symbol Digit Modalities Test and the Low Contrast Letter visual Acuity Test;
- Administration of the MFIS and of the Fatigue Severity Scale;
- Patients satisfying all eligibility criteria will be randomised to the assigned treatment group;
- IP will be dispensed to patients with directions for use. Patients will be reminded to return the unused IP at the next visit;
- Neurophysiological assessments (LTP and recruitment curve) will be performed in patients without relapse enrolled at the centre of the PPD [REDACTED]
- A blood sample will be collected (before receiving corticosteroids) for immune-phenotype and immunometabolic analysis in patients enrolled in the centres of Rome, Naples and Pozzilli;
- A brain MRI will be performed whenever possible, according to local clinical practice;
- Adverse events occurred from the previous visit and/or during this visit will be recorded;

Once all procedures and assessments for this visit are completed, an appointment for the next visit will be made.

Visit 1 (Week 8)

The following procedures and assessments will be performed at this Visit:

- Any change in concomitant medications will be recorded;
- Physical examination including height, weight, BMI, waist circumference, blood pressure, heart rate;
- Neurological examination;
- A blood sample will be collected for haematology and blood chemistry tests, according to local clinical practice;
- A urine sample will be collected for routine urinalysis, according to local clinical practice;
- Administration of the EDSS;
- Administration of the 25-FWT, the 9HPT, the Symbol Digit Modalities Test and the Low Contrast Letter visual Acuity Test;
- Administration of the MFIS and of the Fatigue Severity Scale;
- Neurophysiological assessments (LTP and recruitment curve) will be performed in patients without relapse enrolled at the centre of the PPD
- A blood sample will be collected for immune-phenotype and immunometabolic analysis in patients enrolled in the centres of Rome, Naples and Pozzilli;
- IP will be returned by patients and compliance to therapy will be evaluated.

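### The main recovery tests at Weeks 8, 12 and 24 make no use of the Visit 0 Functional System scores; the chi-square is valid, but pre-specified adjustment could gain power and precision at little cost

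*Combined protocol and SAP*

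**What the plan says.** Section 8.4.2 states that the primary comparison of Week 8 recovery "will be based on descriptive statistics (difference, relative risk and/or odds ratio) and on the chi-square test". No covariate or stratification factor is included. Section 8.4.3 says that the Week 12 and Week 24 recovery comparisons "will be analysed as the main analysis of the primary endpoint".

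An adjusted model does exist. The next paragraph of 8.4.2 plans a logistic regression of Week 8 recovery with "age, sex, current DMT use, disease course, severity of relapse, and random assignment as covariates, to adjust for imbalances between the treatment groups". It is labelled exploratory, and severity of relapse is not defined there or elsewhere.

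Table 1 and the Baseline Visit list in 7.1 include "Administration of the EDSS" at Visit 0 for all patients; 7.1 lists it ahead of randomisation and dispensing. Section 7.3 makes the Functional System scores of the EDSS the instrument for judging recovery. Section 8.4.1 describes these methods as an outline, with full details left to an SAP produced before database lock.

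**The concern.** The depth of the deficit at Visit 0 may well predict whether a patient has recovered by Week 8. If so, an unadjusted comparison leaves explainable variation in the error term, and a chance difference in relapse depth between the arms passes into the crude risk difference. Randomisation is stratified by age and site location only (6.3, 8.1), so the design does not balance severity.

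The exploratory model does not fill the gap. It does not supply the primary test, its severity term is undefined, and two of its other covariates (current DMT use and disease course) should hardly vary, because every patient has RR-MS and is on the same interferon regimen. The documents give no reason for leaving a baseline measure of severity out of the main analysis.

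At stake are some power and some width of the confidence interval in a comparison of 40 patients per arm.

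**Working it through.** **Inputs from 8.1.** Control recovery 40%, D-asp recovery 70%, 40 per arm, one-sided alpha 0.05, stated power 80%.

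**Input not in the documents.** The within-arm correlation rho between the Visit 0 score and recovery. It is assumed, from 0 to 0.5.

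**1. Reproduce the plan's figure.**
- Pooled rate 0.55. Null SE = sqrt(0.55 × 0.45 × 2/40) = 0.1112. Alternative SE = sqrt((0.24 + 0.21)/40) = 0.1061.
- Uncorrected n per arm = (1.645 × sqrt(0.495) + 0.842 × sqrt(0.45))² / 0.09 = 32.9, so 33. With the continuity correction it is 40, as stated.
- Continuity-corrected power at 40 per arm: z = (0.30 − 0.025 − 1.645 × 0.1112)/0.1061 = 0.87, giving 80.7% (79.8% exact).
- Uncorrected power: z = (0.30 − 1.645 × 0.1112)/0.1061 = 1.10, giving 86.5% (85.7% exact).

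The stated 80% therefore holds without any adjustment.

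**2. Effect of adjustment.** Adjusting for a covariate with within-arm correlation rho multiplies the variance of the risk difference by about (1 − rho²), so both SEs shrink by sqrt(1 − rho²). The 95% half-width is 1.96 × 0.1061 × sqrt(1 − rho²). For example, at rho = 0.5 it is 20.8 × sqrt(0.75) = 18.0 points.

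The formula was compared with 6,000 simulated trials per setting (uncorrected chi-square against a covariate-adjusted score test, standard normal covariate, logistic outcome model).

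| rho | Formula power | Gain, formula (points) | Gain, simulation (points) | 95% half-width (points) |
|---|---|---|---|---|
| 0 | 86.5% | 0 | 0.3 | 20.8 |
| 0.1 | 86.8% | 0.3 | 0.6 | 20.7 |
| 0.2 | 87.7% | 1.2 | 2.0 | 20.4 |
| 0.3 | 89.2% | 2.7 | 3.4 (86.2% to 89.6%) | 19.8 |
| 0.4 | 91.3% | 4.8 | 5.7 (86.0% to 91.7%) | 19.1 |
| 0.5 | 93.8% | 7.3 | 8.9 (85.3% to 94.2%) | 18.0 |

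**3. Second simulation.** This used a logistic likelihood-ratio test, 8,000 trials per setting, indexed by R² (the share of outcome variance explained within arm, roughly rho²). One-sided power went from 86.2% to 88.4% at R² about 0.05, from 85.4% to 90.1% at 0.12, and from 85.9% to 94.4% at 0.28. With no prognostic value there was no material change (85.8% against 86.2%).

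**4. Type I error.** With 40% recovery in both arms, the one-sided adjusted score test rejected in 4.8% to 5.4% of trials and the likelihood-ratio test in 4.9% to 5.8%.

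**5. Sidedness.** Section 8.4.1 says that "all statistical hypotheses will be tested at the 5% significance level" against two-sided alternatives unless otherwise specified, while 8.1 is one-sided. On a two-sided uncorrected test, formula power is 78.0% unadjusted, 82.3% at R² = 0.10 and 88.7% at R² = 0.25. The conflict needs settling in its own right and does not alter this point.

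**The case against.** The strongest reply is that this is a preference about efficiency. The chi-square is valid under randomisation, the sample size does not rely on adjustment, and 8.1 calls the study exploratory. All of that stands. A reader might infer that the primary test is wrong or the trial underpowered for want of adjustment; the reproduced 80% shows otherwise on the one-sided basis of 8.1. Nor is a chance imbalance in severity a bias: the type I error and the confidence interval already allow for it.

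The benefit may be small. The documents report neither the prognostic strength nor the distribution of Visit 0 deficits. A reader might take the entry criteria to show a wide spread of severity, but 5.3.1 gives two alternative minimum thresholds, not the ends of a range, and limits pre-relapse EDSS to 0 to 3. A range starting near zero is the only fair one. The simulations are also a favourable case, with a normal covariate and a correctly specified model. A sum of ordinal items mixes long-standing disability with relapse deficit, and adds an ambulation score running to 12 to items running to 5 or 6 (Appendix II). These features could weaken prediction, but they would not make the adjusted analysis invalid.

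A further reply is that baseline status is undefined in 8.1, so Visit 0 might be the reference for recovery and hence part of the outcome. This does not hold up. Section 8.1 describes return to baseline after a relapse that worsened disability, and 8.2.2 places the baseline fatigue assessment during the relapse. Visit 0 therefore measures the deficit. The wording should still be made explicit.

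Finally, a reader might conclude that baseline severity is ignored altogether. It is not, since the exploratory model names it. That softens the point but does not put the information into the main tests.

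**Conclusion.** The point holds as a recommendation on efficiency. The main recovery comparisons at Weeks 8, 12 and 24 are unadjusted and draw nothing from the Visit 0 scores that the trial already collects.

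For 40% versus 70% with 40 per arm and one-sided 0.05, the forgone power ranges from nothing to about 9 points, and the forgone narrowing of the 95% half-width from nothing to 2.8 points (20.8 to 18.0). The gain reaches about 5 points only at a correlation near 0.4. Where in this range the trial falls cannot be told from the documents. The figures assume one roughly linear baseline covariate, complete data and the recovery rates of 8.1.

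**What to change.** In the SAP, before unblinding:

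- Make the main analysis in 8.4.2 a logistic regression of Week 8 recovery on treatment and one covariate: the Visit 0 sum of the seven items used in the endpoint. Table 1 schedules these for every patient. Steps above the pre-relapse value would isolate the relapse deficit better, but Table 1 schedules no pre-relapse Functional System assessment, so that measure could not be relied on for all patients.
- Report the standardised (marginal) risk difference with its confidence interval, and take the test from the same model. The conditional odds ratio is a different quantity and should not replace it. Name the test version; the score test kept close to its nominal level in the simulations above.
- Keep the unadjusted chi-square and crude risk difference as a sensitivity analysis.
- Use the same model at Weeks 12 and 24 in 8.4.3.
- State that recovery is judged against the pre-relapse state, so that the covariate is not part of the outcome definition.

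The cost is SAP wording and a little programming, with no new data or patients. The downside is small: the estimate becomes model-based, and there is little or no gain if the covariate is only weakly prognostic.
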